11.2. Withdrawal from Study Treatment

Each subject has the right to withdraw from the study at any time. In addition, the investigator will discontinue a subject from the study at any time if the investigator considers it necessary for any reason including:

- The investigator believes it is in the best interest of the subject;
- The subject's response to therapy is unsatisfactory, as evidenced by progression of disease while on study drug;
- The subject requires radiotherapy, cancer-related surgery as a result of tumor progression, or alternate anti-neoplastic agents during the study period;
- Noncompliance with the protocol;
- Unacceptable adverse event(s), or
- General or specific changes in the patient's condition render the patient unacceptable for further treatment in the judgment of the investigator.

If, at any time the constraints of this protocol are detrimental to the patient's health and/or patient no longer wishes to continue protocol therapy, protocol therapy shall be discontinued. In this event:

- Notify the Study Chair
- Document the reason(s) for discontinuation of therapy in the study record.
- Follow the patient for relapse, progression, survival, and secondary malignancies or new primaries.

12. STATISTICAL METHODS AND ANALYSIS

This is a phase I/II study in which patients will be enrolled in a standard 3+3 design. Once the maximum tolerated dose is determined, there will be a 17-patient phase II study.

12.1. Phase I study

The maximum tolerated dose (MTD) finding procedure uses the traditional 3+3 cohort method, starting from dose level 0. A dose level will be chosen as the MTD if it has 6 patients, and number of observed DLT is 0 or 1. The MTD is also known as the recommended phase II dose.

Three patients will be enrolled at Dose Level 0 (DL0). Patients will be assessed for DLTs during Cycle 1.

Three patients will initially be entered at DL0.

- If 0/3 DLT is observed, dose escalation will continue to the next upper dose level.
- If $\geq 2/3$ DLTs are observed, then the dose finding procedure will be terminated.
- If 1/3 DLT is observed, then 3 additional patients will be enrolled in the same dose level.

If no DLT is observed from the additional 3 patients, then dose escalation will continue to

the next upper dose level. If any DLT is observed from the 3 additional patients, then the previously lower dose will be chosen as the MTD and the dose finding procedure will be terminated.

Dose escalation will be continued as per Table 2 until a dose with no more than 1/6 DLTs is found and is chosen as the MTD.

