5.2. Treatment Plan

5.2.1 Phase I Study Treatment Plan

Patients will be treated with combination therapy of ibrutinib and venetoclax according to their assigned dose level cohort. Dose escalation is described in Table 2 and the paragraph below.

Each cycle is 28-days. Patients will be monitored for dose limiting toxicity (DLT) weekly during Cycle 1. Patients will receive the combination until progression or unacceptable toxicity. Patients will be followed during therapy through progression until next line of therapy. Questions regarding treatment should be directed to the Study Chair.

Table 2: Dose Level Cohorts

Dose Levels		
Dose Level	Ibrutinib	Venetoclax
0	420 mg	400 mg
1	560 mg	400 mg
2	560 mg	600 mg

*Dose Level 0 is the starting level dose

The MTD finding procedure starts at DL0. Three patients will initially be entered at this dose level.

- If 0/3 DLT is observed, dose escalation will continue to the next upper dose level.
- If $\geq 2/3$ DLTs are observed, then the dose finding procedure will be terminated.
- If 1/3 DLT is observed, then 3 additional patients will be enrolled in the same dose level. If no DLT is observed from the additional 3 patients, then dose escalation will continue to the next upper dose level. If any DLT is observed from the 3 additional patients, then the

previously lower dose will be chosen as the MTD and the dose finding procedure will be terminated.

Dose escalation will be continued as per Table 2 until a dose with no more than 1/6 DLTs is found and is chosen as the MTD. Once the MTD is determined, there will be a 17-patient phase II study at this dose level.

The original design of this study included a Dose Level 3 of Ibrutinib 560 mg and Venetoclax 800 mg. After examining the pharmacokinetic data at Dose Level 2, which showed a significantly increased systemic plasma exposure to ibrutinib, it was determined not to proceed with Dose Level 3. One patient had initiated therapy at Dose Level 3 before the decision was made for closure.

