8. DEFINITION OF DOSE LIMITING TOXICITY

Assessment of DLT will be defined as any non-hematologic or hematologic toxicity listed below that occurs during the first cycle of treatment. Toxicities will be graded according to the National Cancer Institute Common Terminology Criteria for Adverse Events (NCI CTCAE), version 4.03. Patients will be included in the DLT assessment as long as they have received at least 85% of planned doses of each drug or have experienced a DLT any time after the 1st dose. For each patient who did not receive $\geq 85\%$ of therapy, another patient will be enrolled at that dose level.

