12.4. Target Accrual and Study Duration

The real sample size of this study is variable. The minimum required sample size is 6, but this number may change based on the number of DLTs experienced by patients during the phase I portion of the study. The maximum samples size will be 35 patients (= 3 dose levels x 6 patients + 17 patients for expansion). The patient accrual will be closed as soon as the MTD is found and the phase II expansion is completed. We will have conference calls every 2 weeks with all sites with patients enrolled to discuss toxicity in individual cases. The safety data of all patients will be reviewed during the biweekly conference calls, and the stopping rule for the 3+3 cohort scheme will be applied.

The estimated accrual rate is about 2 patients per month. As a result, it will take about 13 months to find and expand the MTD. However, observation of PFS will require longer follow-up. A maximum of 10 years of follow-up is required for all patients. Once the targeted number of patients has been accrued to this study, a notice suspending accrual will be issued to the Group via email broadcast announcing permanent termination of patient accrual within 14 days.

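### The 3+3 bullets in 5.2.1 and 12.1 do not implement 12.1's own 6-patient MTD criterion: step-down can name a level on 3 patients, and 0/3 at Dose Level 2 has no next step

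*Combined protocol and SAP*

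**What the plan says.** Section 12.1 opens with the selection criterion: "A dose level will be chosen as the MTD if it has 6 patients, and number of observed DLT is 0 or 1". It also makes the MTD the recommended phase II dose. Section 5.2.1 has the same bullets and closing sentence, but not that opening criterion.

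The bullets in both sections work as follows:

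- **0/3:** "If 0/3 DLT is observed, dose escalation will continue to the next upper dose level".
- **≥2/3:** dose finding terminates. No dose is named.
- **1/3:** three more patients are treated. With no further DLT, escalation continues. With any further DLT, the "previously lower dose will be chosen as the MTD and the dose finding procedure will be terminated".

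The closing sentence in both sections continues escalation "until a dose with no more than 1/6 DLTs is found and is chosen as the MTD".

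Table 2 now ends at DL2 (ibrutinib 560 mg, venetoclax 600 mg). Section 5.2.1 explains that Dose Level 3 was dropped "After examining the pharmacokinetic data at Dose Level 2, which showed a significantly increased systemic plasma exposure to ibrutinib". It adds: "One patient had initiated therapy at Dose Level 3 before the decision was made for closure". Section 12.4 builds the maximum sample size as "3 dose levels x 6 patients + 17 patients for expansion" and gives a minimum of 6. Section 8 defines who counts: "Patients will be included in the DLT assessment as long as they have received at least 85% of planned doses of each drug", or have had a DLT; others are replaced.

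**The concern.** The criterion and the operating rules should give the same answer, and they do not.

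1. **Step-down.** A lower level can have been cleared on 0/3. If the level above then fails by 1/3 plus a further DLT, the bullet names that lower level and ends dose finding. It is named on 3 patients, against the 6-patient sentence a few lines above.
2. **≥2/3.** The procedure ends with no dose identified.
3. **1/6.** The third bullet escalates after 1/6, while the closing sentence stops there and names the dose.
4. **0/3 at DL2.** The only instruction is to go to a level that has been removed. No bullet treats three more patients at DL2, and nothing says what follows if DL2 is filled to 6 and then has two or more DLTs.

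The recommended dose is the phase I primary objective and fixes the dose for the 17-patient efficacy test. On the account in 5.2.1, escalation ended on pharmacokinetics rather than DLTs, and the raised ibrutinib exposure was seen at DL2 itself. The 6-patient criterion is therefore the remaining numerical tolerability test for that dose.

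**Working it through.** **The plan's own figure.** Section 12.4: 3 × 6 + 17 = 35. This reproduces, and it budgets 18 phase I patients at 6 per level.

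**Inputs.** Cohorts of 3, the bullets and the criterion come from 12.1 and 5.2.1. The documents give no true DLT rates, so those below are assumptions. Write p for the DLT rate at a level and q = 1 − p.

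**Step 1: what a cleared level establishes.** One-sided 95% upper bounds on p (Clopper–Pearson):

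- 0/3: 1 − 0.05^(1/3) = 0.632
- 0/6: 1 − 0.05^(1/6) = 0.393
- 1/6: the p solving q⁶ + 6pq⁵ = 0.05, which is 0.582

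**Step 2: chance of accepting one level.** If 0/3 is taken as enough, P = q³ + 3pq⁵. Under the 6-patient criterion, P = q⁶ + 6pq⁵. The difference is q³ × P(≥2 DLTs in the next 3), where P(≥2 of 3) = 3p²q + p³.

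| Assumed p | 0/3 taken as enough | 6-patient criterion | Difference | P(≥2 of next 3) |
|---|---|---|---|---|
| 20% | 0.512 + 0.197 = 0.709 | 0.262 + 0.393 = 0.655 | 0.053 | 0.104 |
| 30% | 0.343 + 0.151 = 0.494 | 0.118 + 0.303 = 0.420 | 0.074 | 0.216 |
| 40% | 0.216 + 0.093 = 0.309 | 0.047 + 0.187 = 0.233 | 0.076 | 0.352 |

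**Step 3: how often the written step-down bullet names a level on 3 patients, seen from the start of dose finding.** For each level let a = q³ (cleared on 3), b = 3pq⁵ (cleared on 6) and c = 3pq²(1 − q³) (1/3, then a further DLT). Then

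P = a₀c₁ + (a₀ + b₀)a₁c₂.

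For assumed DLT rates at DL0/DL1/DL2:

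- 5/10/20%: 0.857 × 0.066 + 0.974 × 0.729 × 0.187 = 0.056 + 0.133 = 0.19
- 10/20/30%: 0.729 × 0.187 + 0.906 × 0.512 × 0.290 = 0.137 + 0.134 = 0.27
- 15/25/40%: 0.614 × 0.244 + 0.814 × 0.422 × 0.339 = 0.150 + 0.116 = 0.27

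If a ≥2/3 stop is also read as falling back one level, which the text does not say, these become 0.29, 0.45 and 0.48.

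**Step 4: where the trial stands.** A patient could start Dose Level 3 under the bullets only if DL2 had been cleared, on 0/3 or 1/6. If it was 1/6, DL2 already meets the criterion. If it was 0/3 with nobody added, the bullets give no next step.

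**The case against.** The strongest reply is that the intent is clear. 12.1 opens with the 6-patient criterion, the closing sentence in both sections speaks of 1/6, and 12.4 budgets 6 patients at each of three levels. At 0/3 on DL2 the bullets are silent; they do not name DL2. Read with the criterion, the natural next step is three more patients. This stands. A reader might infer that the plan lets DL2 be named on 3 patients, and might note that P(0/3 given cleared) = 1/(1 + 3pq²) is never below 9/13 (69%). The documents do not support that inference. No sentence permits it, and the 69% assumes both that DL2 was cleared and that the criterion was then ignored.

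It is also fair that much of this no longer drives a decision. If DL0 to DL2 were cleared, the 1/6 conflict is inert, and step-down matters only if DL2 is filled and then fails. Patients 4 to 6 at DL2 would receive the same dose either way. Safety is reviewed on calls every two weeks (12.4), with weekly and monthly group meetings and DSMC review every 4 months (14.7).

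What does not fall away is the step-down bullet. It is an explicit rule, not an omission, and it breaks the stated criterion. Nor does review of safety data supply the missing dose-selection step.

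**Conclusion.** The point holds as a mismatch between criterion and operating rules. The step-down bullet contradicts the 6-patient criterion outright. The ≥2/3, 1/6 and 0/3-at-DL2 wording is incomplete or inconsistent. It should be corrected, but it is not fatal, because the intended number can be inferred.

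If the criterion were overlooked, the effect on accepting a level is 5 to 8 percentage points at assumed DLT rates of 20 to 40%. The loss of assurance is larger: an upper bound of 63% rather than 39% or 58%. Both results rest on independent patients with a common DLT rate at each level, and the acceptance probabilities also rest on the assumed rates. DLT counts and evaluable numbers at DL2 are not in the documents. DL2 may already have 6 evaluable patients, and nothing here shows that the gap ever operated.

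**What to change.** In both 5.2.1 and 12.1, replace the closing sentence with:

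> The MTD is the highest level with no more than 1 DLT among 6 evaluable patients (Section 8). 1/6 below DL2 escalates; 1/6 at DL2 names DL2. If DL2 is cleared with 0/3, 3 more patients are treated before it is named. If any level has ≥2 DLTs, escalation stops and the level immediately below is the candidate, filled to 6 if it has only 3; if it then has ≥2 DLTs, the same rule applies to the next level down. If DL0 has ≥2 DLTs, no MTD is declared.

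Limit the 0/3 escalation bullet to DL0 and DL1. Bring the ≥2/3 bullet and the step-down sentence into line with the text above. If DL2 already has 6 evaluable patients, record that, and none need be added there.

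The cost is wording in two sections and up to 3 patients per level filled: 0 to 3 at DL2, and more below it only if the level above fails. The most that could be added is 3 × 3 = 9, within the 18 budgeted, so the maximum of 35 stands. Under 12.2, patients treated at the MTD who meet the phase II criteria count toward the 17, so confirming DL2 need not enlarge the trial.

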12.2. Phase II Study

Once the MTD, also the known as the recommended phase II doses are determined, the phase II portion of the study will open to potentially 17 patients with relapsed or refractory follicular lymphoma at this dose level. A Simon's Minimax 2-stage design will be used to test the null hypothesis that the response rate is at most 30% against an alternative response rate of 60% (a desirable rate). This design assumes that current individual therapies for this group of patients would have response rate about 30% and it is hoped that the Ibrutinib and Venetoclax would improve the response rate to 60% or more. In Stage 1, 10 patients will be enrolled. The study will proceed to Stage 2 if there are 3 or more responders, otherwise the study will be stopped for futility. In Stage 2, an additional 7 patients will be enrolled for a total of 17 patients and we would accept Ibrutinib and Venetoclax for further studies if there are at least 9 responders out of 17 patients. This design would have 80% statistical power for detecting the advantage in response rate for Ibrutinib and Venetoclax at a statistical significance level of 5% (one-sided). If the combination of Ibrutinib and Venetoclax is actually not effective, there is a 0.04 probability of concluding that it is (targeted value is 0.05). If the combination is actually effective, there is a 0.199 probability of concluding that is not (the targeted value is 0.2).

The 17 patients for the phase II portion will include the FL patients who are treated at the MTD level in phase I and who satisfy the phase II enrollment criteria.

Descriptive statistics (mean, median, n, min, max, std, etc.) will be used to summarize patients' demographics as well as prognostic information. Complete response rate and overall response rate will be estimated for each dose level as per the revised Lugano Response Criteria for Non-Hodgkin Lymphoma with their 90% exact Binomial confidence intervals (Appendix VI). [24] Progression-free survival (defined as time between enrollment and disease progression or death) and overall survival (defined as time between enrollment and death) with their 95% confidence intervals will be estimated by Kaplan-Meier method for the whole number of patients in this study and at the MTD.

12.3. Toxicity Evaluation

Ineligible patients will be replaced by new eligible patients during both phases of the study and will be excluded in the data analysis. Ineligible patients are defined as patients who were initially believed to be eligible, but with full screening have been found to be ineligible.

Toxicity (attribute and grade) will be summarized for each dose level as per the NCI Common

Terminology Criteria for Adverse Events (CTCAE Version 4.03) for all patients who receive at least one dose of study treatment.

12.4. Target Accrual and Study Duration

The real sample size of this study is variable. The minimum required sample size is 6, but this number may change based on the number of DLTs experienced by patients during the phase I portion of the study. The maximum samples size will be 35 patients (= 3 dose levels x 6 patients + 17 patients for expansion). The patient accrual will be closed as soon as the MTD is found and the phase II expansion is completed. We will have conference calls every 2 weeks with all sites with patients enrolled to discuss toxicity in individual cases. The safety data of all patients will be reviewed during the biweekly conference calls, and the stopping rule for the 3+3 cohort scheme will be applied.

The estimated accrual rate is about 2 patients per month. As a result, it will take about 13 months to find and expand the MTD. However, observation of PFS will require longer follow-up. A maximum of 10 years of follow-up is required for all patients. Once the targeted number of patients has been accrued to this study, a notice suspending accrual will be issued to the Group via email broadcast announcing permanent termination of patient accrual within 14 days.

12.5. Correlative Science Statistical Considerations

12.5.1. Mutations of Resistance

The frequency table will be used to summarize patients' clinical outcome status (partial or complete remission and progression). Fisher's Exact test will be used to assess the relationship between the clinical outcomes and the occurrence of new mutations or alterations in the genome.

12.5.2. BCL-2 Family Proteins

Descriptive statistics (including mean, median, std, min, max) will be used to summarize the H-score assessment of individual BCL-2 family member proteins. The H-score will then be categorized, and Fisher's Exact test will be used to explore its relationship with varying expression of BCL-2 family member proteins.

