2.3 Exploratory Objectives

- To evaluate mutations of resistance via next-generation sequencing to the regimen when administered in combination in relapsed and refractory follicular lymphoma
- To evaluate for an association between BCL-2 and other family member protein levels of expression and efficacy of the regimen

- To evaluate the feasibility of developing tumor cell cultures from bone marrow aspirates with lymphomatous involvement in order to better characterize activity of the combination

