10.2. BCL-2 Family Proteins

Levels of expression of various BCL-2 family member proteins will be assessed on tumor samples from patients prior to treatment, on bone marrow biopsy samples after achieving a complete response, and tumor samples at progression. Assessments will be performed on bone marrow biopsy core samples of patients with lymphomatous involvement. One centimeter of the core biopsy will be submitted to the Lombardi Comprehensive Cancer Center

Histopathology and Tissue Shared Resource (HTSR) for processing. The presence of tumor will be assessed by H&E. Sections will be stained by the HTSR for BCL-2 family proteins including BCL-2, MCL-1, BIM, and BCL-XL. The stained slides will be subsequently transported to the Department of Pathology for H-score assessment of individual BCL-2 family member proteins. Samples will be reviewed independently by two hematopathologists ([name]; [name]). If the bone marrow is not involved, the patient may be recommended to undergo a biopsy of an affected lymph node or other disease-involved area as determined by pretreatment staging PET-CT. Alternatively, if tissue is already available from a recent biopsy of an affected area, it may be submitted. These patients will only undergo a follow up biopsy if they experience a progression on study.

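### Section 12.5.2 cuts the H-score at unstated points for Fisher's exact test and names no efficacy outcome; a pre-treatment rank comparison by response costs nothing and is usually more powerful

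*Combined protocol and SAP*

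**What the plan says.** The exploratory objective in section 2.3 is "To evaluate for an association between BCL-2 and other family member protein levels of expression and efficacy of the regimen".

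Section 10.2 lists the stains as "BCL-2 family proteins including BCL-2, MCL-1, BIM, and BCL-XL", so at least four proteins are scored. On the reading it says "Samples will be reviewed independently by two hematopathologists", with no rule for combining the two readings. The same section takes samples at three times: before treatment, once a complete response is reached, and at progression.

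Section 12.5.2 first treats the score as numeric: "Descriptive statistics (including mean, median, std, min, max) will be used to summarize the H-score assessment". It then says "The H-score will then be categorized, and Fisher's Exact test will be used to explore its relationship", and the sentence ends by naming protein expression as the other variable: "explore its relationship with varying expression of BCL-2 family member proteins". It states no cutpoints, number of categories, sampling time or clinical outcome. No other section names a test on the score itself. Section 12.5.3 speaks of possible correlations between response and expression pattern, but under cell cultures and without a method.

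On numbers, section 12.4 says "The maximum samples size will be 35 patients" and section 12.2 says "an additional 7 patients will be enrolled for a total of 17 patients".

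**The concern.** Two things in one sentence do not serve the objective.

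First, a graded score is reduced to categories before testing. In a sample this small that usually gives up power, and the answer then depends on a cut that the plan does not fix.

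Second, the comparison named is between the H-score and BCL-2 family expression. The H-score is the measure of that expression, so the sentence is either circular or compares one protein with another. Neither answers whether expression relates to efficacy, and the right test cannot be chosen until the outcome is named.

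What is at stake is the yield of biopsies already being taken. Dose, stopping and the primary conclusion are not involved.

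**Working it through.** **1. Inputs from the documents.** Phase II N = 17 (section 12.2). Maximum N = 3 × 6 + 17 = 35 (section 12.4). Evaluable tissue may be fewer: the enrolment marrow can be waived (section 4.2), marrow cores are scored only if involved, though other tissue may substitute (section 10.2), and the correlative study is called optional (section 14.2).

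**2. The plan's own figure.** Section 12.5.2 gives no sample size, power or error rate. The only design calculation is the Simon minimax design behind N = 17. Let X₁ be responders among the first 10 and X₂ among the next 7. P(accept) = Σ over x₁ = 3 to 10 of P(X₁ = x₁) · P(X₂ ≥ 9 − x₁). At a response rate of 0.30 this is 0.0402. At 0.60 it is 0.8008, so the type II error is 1 − 0.8008 = 0.1992. The plan states 0.04 and 0.199, so N = 17 is sound.

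**3. Large-sample loss.** Under normality the efficiency relative to the t-test is 2/π for a median split and 3/π for the rank-sum test. The ratio is (2/π)/(3/π) = 2/3, so a median split loses about one third of the information.

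**4. Actual size of Fisher's test at N = 17.** Put 8 patients in the high group and let a be the responders among them. With n₁ responders and n₂ non-responders, P(a) = C(n₁,a)·C(n₂,8−a)/C(17,8), and C(17,8) = 24,310.

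- 9 vs 8: it rejects for a ≤ 1 or a ≥ 7. Size = (1 + 72 + 288 + 9)/24,310 = 370/24,310 = 0.015.
- 10 vs 7: it rejects for a ≤ 2 or a ≥ 7. Size = (10 + 315 + 840 + 45)/24,310 = 1,210/24,310 = 0.0498.
- 11 vs 6: it rejects for a ≤ 3 or a = 8. Size = (55 + 990 + 165)/24,310 = 0.0498, nearly all in one tail.

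So Fisher's test is conservative at some splits and not at others, and at 11 vs 6 its power depends strongly on direction.

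**5. Power.** Assumptions not in the documents: response vs no response as the outcome, untied normal scores, a 1.25 SD shift and the responder splits. Tests are two-sided at 5%, with 20,000 simulated trials per setting (standard error at most 0.004). At odd N the two Fisher values are for the less and the more favourable combination of direction and side on which the middle patient falls.

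| Responders vs non-responders | Rank-sum | Median split + Fisher |
|---|---|---|
| 9 vs 8 | 0.63 | 0.22 / 0.40 |
| 10 vs 7 | 0.61 | 0.41 / 0.58 |
| 11 vs 6 | 0.60 | 0.27 / 0.60 |
| 12 vs 5 | 0.56 | 0.29 / 0.40 |
| 15 vs 15 | 0.89 | 0.68 |
| 16 vs 14 | 0.89 | 0.52 |
| 18 vs 12 | 0.88 | 0.47 |
| 18 vs 17 | 0.94 | 0.75 / 0.85 |
| 21 vs 14 | 0.92 | 0.69 / 0.84 |
| 24 vs 11 | 0.89 | 0.63 / 0.71 |

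**6. Other cuts and a smaller shift.** At 1.0 SD, averaged over splits and directions, power for the rank test, then Fisher with a median cut, a top-third cut and tertiles:

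- N = 17: 43%, 25%, 20%, 25%.
- N = 35: 77%, 55%, 43%, 58%.
- N = 10 (little tissue): 22%, 15%, 7%, 4%.

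**7. Dependence on the cut.** At 9 vs 8, moving the single middle patient from one category to the other changes Fisher's power from 0.40 to 0.22.

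**The case against.** The analysis is exploratory, nothing is decided on it, and the uncategorised score is already summarised. Even the rank test has only about 43% power at N = 17 for a 1.0 SD shift, so neither p-value would carry much weight. The shift, the normal scores and the splits are assumptions, although a check with tied scores showed a similar loss. All of this stands. It sets the severity and is why the fix asks for an estimate with an interval.

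The gain is also not uniform. The 10 vs 7 split is the one nearest the 60% alternative at 17 patients, and there the more favourable arrangement gives 0.61 against 0.58. At 11 vs 6 the gain can vanish. That stands too.

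Three stronger readings are tempting and are not supported.

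- A reader might infer that Fisher's test is always very conservative here. Its size is 0.0498 at 10 vs 7 and 11 vs 6.
- A reader might infer that the p-value will be invalid because the cut will be picked from the outcomes. The plan says only that the score will be categorised. If the cut with the smallest p-value were chosen, with at least 3 patients on each side, the 5% error would become about 16 to 18% at N = 17 and 23% at N = 35 (21 vs 14), per protein. That is a possibility the text leaves open, not something it plans.
- A reader might infer that only the test needs changing. Section 12.5.2 never names response, so moving to a responder comparison changes what is compared and should be declared as such.

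**Conclusion.** The point holds as a free improvement of minor weight. On the assumptions above, testing the score itself gives power of about 0.6 against about 0.22 to 0.60 at 17 patients, and about 0.9 against about 0.47 to 0.85 at 30 to 35. The gain ranges from near zero to large, depending on the split, the direction and the cut. The missing efficacy outcome is the more basic fault in the sentence and does not depend on any simulation. The primary result is untouched. Testing at least four proteins carries a chance of about 1 − 0.95⁴ = 19% of one or more false positives if they are independent at 5%; neither test changes that.

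**What to change.** Replace the categorise-and-test sentence in section 12.5.2 with:

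> For each protein, the pre-treatment H-score (mean of the two readers) will be compared between responders (CR or PR by Lugano criteria) and non-responders by the exact (permutation, tie-adjusted) Wilcoxon rank-sum test, with the Hodges-Lehmann difference and 95% CI. Scores at complete response and at progression will be summarised descriptively, and any categorised table is descriptive only.

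Restricting the test to pre-treatment samples keeps one observation per patient and avoids later samples that exist only in patients selected by their outcome. Averaging the two readers is a proposal, since section 10.2 leaves the rule open; another rule would do if fixed in advance. If categories are kept for description, state their cutpoints beforehand.

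The cost is an edit to one sentence, which also corrects the comparison. It needs no additional patients, samples, assays or staff.
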